| Abnormal, Clinically Significant | xx (xx.x%) | xx (xx.x%) | xx (xx.x%) | xx (xx.x%) |

Listing Shells

Listing 1: Subject Disposition - All Subjects

Listing 2: Reasons not Eligible – Screen Failures

Listing 3: Protocol Deviations

Listing 4: Demographics Data

Listing 5: Medical History -Screening

Listing 6: Physical Exam -Screening

Listing 7: Height/Weight-Screening

Listing 8: Genetic Tests

Listing 9: Infectious Disease Serology-Screening

Listing 10: Pregnancy Test/Birth Control Methods (Females only) -Screening and Day-1

Listing 11: Endoscopy

Listing 12: GI Signs and Symptoms

Listing 13: Stool Consistency

Listing 14: Plasma Concentrations

Listing 15: Pharmacokinetic Parameters

Listing 16: Adverse Events

Listing 17: Adverse Events Leading to Subject Withdrawal from Study

Listing 18: Serious Adverse Events

Listing 19: Blood Chemistries

Listing 20: Hematology

Listing 21: Coagulation

Listing 22: Urine Drug Screen

Listing 23: Vital Signs

Listing 24: Electrocardiogram

Listing 25: Prior and Concomitant Medications

Listing 1: Subject Disposition - All Subjects

| Subject ID | Date of Consent | Eligible | Date of random-ization | Treatment Group | Safety Analysis Set | PK Analysis Set | Study Completion | (Day) Date of Study Completion or Early Withdrawal | Reason for Early Withdrawal |
|------------|-----------------|----------|------------------------|-----------------|---------------------|-----------------|------------------|--|-----------------------------|
| xxxx | mm/dd/yyyy | Y/N | mm/dd/yyyy | | Yes | Yes | Yes | (xx) mm/dd/yyyy | xxxxxx |
| | | | | | No | No | No | | |
| | | | | | | | | | |
| | | | | | | | | | |

Note: Day is relative to Study Day 1.

Listing 2: Reasons not Eligible – Screen Failures

| Subject ID | Criterion Type | Criterion |
|------------|--------------------|-----------|
| xxxx | Inclusion Criteria | |
| | Exclusion Criteria | |

Listing 3: Protocol Deviations

| Subject ID | Treatment | Deviation Date | Protocol Deviation | Other Details |
|------------|-----------|----------------|--------------------|---------------|
| xxxx | | mm/dd/yyyy | | |
| | | | | |
| | | | | |
| | | | | |

Note: Only subjects with protocol deviation are listed.

Listing 4: Demographics Data

| Subject | Treatment | Gender at Birth | Age (yrs) | Ethnicity | Race |
|---------|-----------|-----------------|-----------|------------------------|---|
| XXXX | | Male | xx | Hispanic or Latino | American Indian or Alaska Native |
| | | Female | | Not Hispanic or Latino | Asian |
| | | | | Unknown | Native Hawaiian or Other Pacific Islander |
| | | | | | Black or African American |
| | | | | | White |
| | | | | | Other |
| | | | | | Unknown |

Listing 5: Medical History -Screening

| Subject | Treatment | Medical History Term | Start Date | Ongoing |
|---------|-----------|----------------------|------------|---------|
| XXXX | | XXXX | | |
| | | | mm/dd/yyyy | No |
| | | | | Yes |
| | | | | |

Listing 6: Physical Exam -Screening

| Subject | Treatment | Exam Date | Any abnormal finding during the physical exam? | Describe |
|---------|-----------|------------|--|----------|
| XXXX | | mm/dd/yyyy | Yes | XXXXXXXX |
| | | | No | |
| | | | | |
| | | | | |

Listing 7: Height/Weight-Screening

| Subject ID | Treatment | Exam Date | Height (cm) | Weight (kg) | Body Mass Index (kg/m ²) |
|------------|-----------|------------|-------------|-------------|--------------------------------------|
| xxxx | | mm/dd/yyyy | xxx | xx | |
| | | | | | |
| | | | | | |
| | | | | | |

Listing 8: Genetic Tests -Clinic Intake

| Subject ID | Group | Exam Date | Any Blood Collection Problems? /Specify |
|------------|-------|------------|---|
| xxxx | | mm/dd/yyyy | Y/xxxx |
| | | | |
| | | | |
| | | | |

Listing 9: Infectious Disease Serology-Screening

| Subject ID | Group | HBSAg | Hep C Antibody | HIV-1 antibody | HIV-2 antibody | HIV-1 p24 | HIV-2 p24 | COVID antigen |
|------------|-------|---------|----------------|----------------|----------------|-----------|-----------|---------------|
| xxx | | 1, 2, 3 | mm/dd/yyyy | mm/dd/yyyy | xx | xx | | |
| | | | | | | | | |
| | | | | | | | | |
| | | | | | | | | |

Listing 10: Pregnancy Test/Birth Control Methods (Females only) -Screening and Day-1

| Subject ID | Group | Pregnancy Test Performed? | Pregnancy Test Date | Pregnancy Result | Methods of birth control |
|------------|-------|---------------------------|---------------------|------------------|--------------------------|
| xxx | | Not Done | mm/dd/yyyy | Negative | |
| | | | | Positive | |
| | | | | | |

Programming note: Only indicate birth control methods that were indicated as Yes

Listing 11: Endoscopy

| Subject ID | Group | Visit | Date | Was Overall Video Quality Acceptable? | Reason Not Acceptable | Any Microscopic Abnormalities? | Specify Microscopic Abnormalities | Any Macroscopic Abnormalities? | Specify Macroscopic Abnormalities |
|------------|-------|-----------|------------|---------------------------------------|-----------------------|--------------------------------|-----------------------------------|--------------------------------|-----------------------------------|
| xxxx | | Screening | mm/dd/yyyy | -30 | xxx | xxx | xxx | xx | xx.x |
| | | Day -1 | | -15 | | | | | |
| | | | | +15 | | | | | |
| | | | | +30 | | | | | |

Listing 12: GI Signs and Symptoms

| Subject ID | Group | Visit | Date | Symptoms | Present? |
|------------|-------|-----------|------------|----------|----------|
| xxxx | | Screening | mm/dd/yyyy | | |
| | | Day -1 | | | |
| | | | | | |
| | | | | | |

Listing 13: Stool Consistency

| Subject ID | Group | Visit | Date/ Time | Frequency of Stools per Day | Consistency of Stools per Day | Category/Symptom | Severity |
|------------|-------|-----------|------------|-----------------------------|-------------------------------|------------------|----------|
| xxxx | | Screening | mm/dd/yyyy | | | | |
| | | Day -1 | | | | | |
| | | | | | | | |
| | | | | | | | |

Listing 14: Plasma Concentrations

| Subject ID | Group | Nominal Timepoint | Date | Time | DCUKA (ng/mL) | 8-OH DCUKA (ng/mL) |
|------------|-------|-------------------|------------|-------|---------------|--------------------|
| xxxx | | | mm/dd/yyyy | hh:mm | xx.x | xx.x |
| | | | | | | |
| | | | | | | |
| | | | | | | |

Note: Nominal timepoints include: 15 minutes prior to dosing, then at 0.25, 0.5, 1, 1.5, 2, 4, 8, 12, 24, and 48 hours after dosing.

Listing 15: Pharmacokinetic Parameters

| Subject ID | Group | C _{max} (ng/mL) | t _{max} (hr) | AUC ₀₋₄ (h*ng/mL) | AUC ₀₋₈ (h*ng/mL) | AUC _{0-last} (h*ng/mL) | AUC _∞ (h*ng/mL) | λ _z | t _{1/2} (hr) |
|------------|-------|--------------------------|-----------------------|------------------------------|------------------------------|---------------------------------|----------------------------|----------------|-----------------------|
| xxxx | | xx.x | xx.x | xx.x | xx.x | xx.x | xx.x | xx.x | xx.x |
| | | | | | | | | | |
| | | | | | | | | | |
| | | | | | | | | | |

Listing 16: Adverse Events

| Subject ID | Treatment Group | Adverse Event (Verbatim) S: SOC P: PT Term | Start Date/ Day | Stop Date/ Day | Duration in Days | Severity | Relationship | Actions Taken | Outcome | Serious |
|------------|-----------------|---|--------------------|-------------------|---------------------|----------|--------------|---------------|---------|---------|
| xxx | | Verbatim | mm/dd/yyyy | mm/dd/yyyy | xx | 1 | 1 | 1 | 1 | Yes |
| | | S: xxxx | xx | xx | | 2 | 2 | 2 | 2 | No |
| | | P: xxxx | | | | 3 | 3 | 3 | 3 | |
| | | | | | | 4 | 4 | 4 | 4 | |
| | | | | | | | 5 | 5 | 5 | |
| | | | | | | | | 6 | | |

Notes: Day is relative to Study Day 1.

Severity: 1=Grade 1; 2= Grade 2; 3= Grade 3, 4= Grade 4.

Relationship: 1= Not related; 2=Unlikely related; 3=Possibly related; 4=Related

Action Taken Due to AE: 1=None; 2=Treated with Drugs; 3=Non-drug treatment; 4=ER/Outpatient visit; 5=Hospitalization; 6=Referral for treatment; 7=Other

Outcome: 1=Resolved without sequelae; 2= Ongoing; 3= Recovered with sequelae; 4=Fatal; 5=Unknown

Programmer's Note: If "Were any AEs reported?" checkbox=No, then display "None Reported" in the Adverse Event column and SOC/PT column. If an AE started and stopped the same day, the duration is 1 day.

Listing 17: Adverse Events Leading to Subject Withdrawal from Study

| Subject ID | Treatment Group | Adverse Event (Verbatim) S: SOC P: PT Term | Start Date/Day | Stop Date/Day | Duration in Days | Severity | Relationship | Actions Taken | Outcome | Serious |
|------------|-----------------|---|----------------|---------------|------------------|----------|--------------|---------------|---------|---------|
| xxx | | Verbatim | mm/dd/yyyy | mm/dd/yyyy | | 1 | 1 | 1 | 1 | Yes |
| | | S: xxxx | xx | xx | | 2 | 2 | 2 | 2 | No |
| | | P: xxxx | | | | 3 | 3 | 3 | 3 | |
| | | | | | | 4 | 4 | 4 | 4 | |
| | | | | | | | 5 | 5 | 5 | |
| | | | | | | | | 6 | | |

Notes: Day is relative to Study Day 1.

Severity: 1=Grade 1; 2= Grade 2; 3= Grade 3, 4= Grade 4.

Relationship: 1= Not related; 2=Unlikely related; 3=Possibly related; 4=Related

Action Taken Due to AE: 1=None; 2=Treated with Drugs; 3=Non-drug treatment; 4=ER/Outpatient visit; 5=Hospitalization; 6=Referral for treatment; 7=Other

Outcome: 1=Resolved without sequelae; 2= Ongoing; 3= Recovered with sequelae; 4=Fatal; 5=Unknown

Programmer's Note: If "Were any AEs reported?" checkbox=No, then display "None Reported" in the Adverse Event column and SOC/PT column. If an AE started and stopped the same day, the duration is 1 day.

Listing 18: Serious Adverse Events

| Subject ID | Treatment Group | SAE Verbatim S: SOC P: PT | Start Date/ Day | Stop Date/ Day | SAE Category | Severity | Relationship |
|------------|-----------------|---------------------------------|--------------------|-------------------|--|----------|--------------|
| xxx | | Verbatim | mm/dd/yyyy | mm/dd/yyyy | Death | 1 | 1 |
| | | S: XXX | Xx | Xx | Life-threatening | 2 | 2 |
| | | P: XX | | | Hospitalization | 3 | 3 |
| | | | | | Disability | 4 | 4 |
| | | | | | Congenital Anomaly/Birth Defect | 5 | 5 |
| | | | | | Required Intervention to Prevent Permanent Impairment / Damage | | |
| | | | | | Other | | |

| Subject ID No. | SAE | Continued Study Participation | Study Drug Start Date | Date of last administration of study drug prior to SAE | SAE Abated after study drug stopped? | Continued study drug Administration | SAE reappeared after rechallenge? | Outcome |
|----------------|----------|-------------------------------|-----------------------|--|--------------------------------------|-------------------------------------|-----------------------------------|---------|
| xxx | Verbatim | Yes | mm/dd/yyyy | mm/dd/yyyy | Yes | Yes | Yes | 1 |
| | | No | | | No | No | No | 2 |
| | | | | | n/a | | n/a | 3 |

Notes: Day is relative to Study Day 1.

Severity: 1=Grade 1; 2= Grade 2; 3= Grade 3, 4= Grade 4.

Relationship: 1= Not related; 2=Unlikely related; 3=Possibly related; 4=Related

Action Taken Due to AE: 1=None; 2=Treated with Drugs; 3=Non-drug treatment; 4=ER/Outpatient visit; 5=Hospitalization; 6=Referral for treatment; 7=Other

Outcome: 1=Resolved without sequelae; 2= Ongoing; 3= Recovered with sequelae; 4=Fatal; 5=Unknown

Listing 19: Blood Chemistries

| Subject ID | Group | Visit | Visit Date | Test Name | Result | Units | Evaluation |
|------------|-------|-------|------------|----------------------|--------|-------|---------------|
| xxxx | | | mm/dd/yyyy | ALT | | | WNL |
| | | | | Albumin | | | Abnormal, NCS |
| | | | | Alkaline phosphatase | | | Abnormal, CS |
| | | | | AST | | | |
| | | | | Total bilirubin | | | |
| | | | | Direct bilirubin | | | |
| | | | | BUN | | | |
| | | | | Calcium | | | |
| | | | | Chloride | | | |
| | | | | Cholesterol | | | |
| | | | | Creatinine | | | |
| | | | | GGT | | | |
| | | | | Glucose | | | |
| | | | | Phosphate | | | |
| | | | | Potassium | | | |
| | | | | Sodium | | | |
| | | | | xxxxx | | | |
| | | | | xxxxx | | | |

Listing 20: Hematology

| Subject ID | Group | Visit | Visit Date | Test Name | Result | Units | Evaluation |
|------------|-------|-----------|------------|------------|--------|-------|---------------|
| xxxx | | Screening | mm/dd/yyyy | Hematocrit | | | WNL |
| | | Day 4 | | Hemoglobin | | | Abnormal, NCS |
| | | Week 4 | | RBC | | | Abnormal, CS |
| | | Week 8 | | WBC | | | |
| | | Week 12 | | Platelets | | | |
| | | | | xxxxxx | | | |

Listing 21: Coagulation

| Subject ID | Group | Visit | Visit Date | Test Name | Result | Units | Evaluation |
|------------|-------|-----------|------------|------------|--------|-------|---------------|
| xxxx | | Screening | mm/dd/yyyy | Fibrinogen | | | WNL |
| | | | | PT | | | Abnormal, NCS |
| | | | | PTT | | | Abnormal, CS |
| | | | | xxxx | | | |

Listing 22: Urine Drug Screen

| Subject ID | Group | Visit Date | Visit | AMP | Barb | Benzos | Coc | Opiates | Canab | Phen | Prop | Meth | Fen | Mor |
|------------|-------|------------|-------|-----|------|--------|-----|---------|-------|------|------|------|-----|-----|
| XXXX | | mm/dd/yyyy | | P | P | P | P | P | P | P | P | P | P | P |
| | | | | N | N | N | N | N | N | N | N | N | N | N |
| | | | | UNK | UNK | UNK | UNK | UNK | UNK | UNK | UNK | UNK | | |
| | | | | | | | | | | | | | | |
| | | | | | | | | | | | | | | |

P=positive; N=negative

AMP=amphetamine, , Barb=barbiturates Benzos=benzodiazepines, Coc=cocaine, Canab=cannabinoids, Phen=phencyclidine, Prop=propoxyphene, Fen=Fentanyl, Mor=Morphine

Listing 23: Vital Signs

| Subject ID | Group | Visit Date | Visit | Timepoint | Heart Rate (beats/min) | Systolic Pressure (mmHg) | Diastolic Pressure (mmHg) | Respiratory Rate (breaths/ min) | Temperature (°F) |
|------------|-------|------------|-------|-----------|---------------------------|--------------------------------|---------------------------------|--|---------------------|
| XXXX | | mm/dd/yyyy | | | xxx | xxx | xxx | | |
| | | | | | | | | | |
| | | | | | | | | | |
| | | | | | | | | | |
| | | | | | | | | | |

Listing 24: Electrocardiogram

| Subject ID | Group | Visit Date | Visit | Timepoint | Heart Rate (beats/min) | RR Interval (Sec) | QT Interval (msec) | QTcF (msec) | Interpretation |
|------------|-------|------------|-------|-----------|---------------------------|----------------------|--------------------------|----------------|----------------|
| xxxx | | mm/dd/yyyy | | | xxx | xxx | xxx | | |
| | | | | | | | | | |
| | | | | | | | | | |
| | | | | | | | | | |
| | | | | | | | | | |

Listing 25: Prior and Concomitant Medications

| Subject ID | Group | Prior Med? | Verbatim Medication Name | Indication | Route | Frequency | Dose | Start Date | Stop Date | Continuing? /Used to Treat AE? |
|------------|-------|------------|--------------------------|------------|--------|-----------|--------|-------------|-------------|--------------------------------|
| xxxx | | Yes | xxx | xxxxxx | xxxxxx | xxxxxx | xxxxxx | dd/mmm/yyyy | dd/mmm/yyyy | Yes /No |
| xxxx | | No | xxx | | | | | | | No |
| | | | | | | | | | | |
| | | | | | | | | | | |

Figure Shells

LIST OF FIGURES

| | |
|---|-----|
| Figure 1: Mean (SD) Chemistry Values Over Time | 111 |
| Figure 2: Mean (SD) Hematology Values Over time | 111 |
| Figure 3: Mean (SD) Vital Signs Over Time | 111 |
| Figure 4: Mean (SEM) Plasma Concentrations Over Time | 111 |
| Figure 5: Individual Subjects Plasma Concentrations Over Time | 111 |

Figure 1: Mean (SD) Chemistry Values Over Time

X-axis – Days – Y Axis – mean standard deviation for each chemistry value over time – all groups

Figure 2: Mean (SD) Hematology Values Over time

X-axis – Days – Y Axis – mean standard deviation for each hematology value over time – all groups

Figure 3: Mean (SD) Vital Signs Over Time

X-axis – Days – Y Axis – mean standard deviation for each vital sign value over time – all groups

Figure 4: Mean (SEM) Plasma Concentrations Over Time

X-axis – Days – Y Axis – mean standard error of the mean for each plasma concentrations of DCUKA and 8-OH DCUKA values (on separate graphs) over time plotted on linear and log scales – all groups

Figure 5: Individual Subjects Plasma Concentrations Over Time

X-axis – Days – Y Axis – DCUKA and 8-OH DCUKA plasma concentrations for each subject

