## **8.13. Subject and Study Discontinuation and Stopping Criteria**

### **8.13.1. Discontinuation of Individual Subjects**

Each subject has the right to withdraw from the study at any time. In addition, the investigator may discontinue a subject from the study at any time if the investigator considers it necessary for any reason, including the occurrence of an AE or noncompliance with the protocol. Subjects who withdraw from the study will not be replaced unless it is mutually agreed upon, in writing, between the investigator and the sponsor.

Some specific considerations for replacement of subjects include:

1. If a subject is considered eligible for the study but does not receive any investigational product, another subject will be enrolled to ensure that each cohort has the target number of subjects.
2. If a subject is randomized to the active group but withdraws from the study before the Day 3 clinic release procedures are performed, then a replacement subject may be considered.
3. If a subject for some reason is missing safety measures such as clinical laboratory assessments, vital signs, or FOBT.
4. If a subject for some reason is missing blood samples for PK measurements such that PK cannot be determined.

If a subject withdraws or is discontinued from the study, the reason(s) for the discontinuation from the study will be recorded and a physical examination, body weight, vital signs measurement, ECG, laboratory analyses, Stool Consistency Questionnaire, GI Symptoms Checklist, and AEs will be performed as soon as possible after discontinuation from the study. Additional blood samples for drug measurement may be collected at the time of discontinuation from subjects who are discontinued due to AEs; the clock time, and date the sample was taken will be recorded.

If a subject is discontinued from the study with an ongoing AE or an unresolved laboratory result that is significantly outside of the reference range, the investigator will attempt to provide follow-up until a satisfactory clinical resolution of the laboratory result or AE is achieved.

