### 11.3. Clinical Laboratory Tests

Clinical laboratory tests (Table 8) will be performed at the UCSD Medical Center clinical laboratory. The laboratory should be directly regulated by the College of American Pathologists (CAP) or Clinical Laboratory Improvement Act (CLIA) guidelines. The laboratory will need to provide a copy of current certification. Additional laboratory samples may be taken at the discretion of the investigator if the results of any tests fall outside reference ranges or clinical symptoms necessitate additional testing to ensure safety.

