9.7 Clinical Laboratory Data

Clinical laboratory test results, urine drug screen results, and pregnancy test results will be reported as summary statistics for each assessment time point. Clinical chemistry, amylase, lipase, hematology, coagulation, urinalysis, FOBT, urine drug screen results, and pregnancy test results will be presented as summary statistics and change from baseline. In addition, change from baseline (shift tables) will also be presented for clinical chemistry, amylase, lipase, hematology, and coagulation data.

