| Repeat for Treatment, Inpatient Follow-up, Clinic Discharge, Outpatient Follow-up and Earl termination | Epigastric pain/discomfort (dyspepsia) | xx.x (xx.xx) | xx.x (xx.xx) | xx.x (xx.xx) | xx.x (xx.xx) | xx.x (xx.xx) |
| | Fatigue | xx.x | xx.x | xx.x | xx.x | xx.x |
| | Light headedness | (xx-xx) | (xx-xx) | (xx-xx) | (xx-xx) | (xx-xx) |
| | Postural dizziness | xx (xx.x%) | xx (xx.x%) | xx (xx.x%) | xx (xx.x%) | xx (xx.x%) |
| | Syncope | xx (xx.x%) | xx (xx.x%) | xx (xx.x%) | xx (xx.x%) | xx (xx.x%) |
| | Nausea | xx (xx.x%) | xx (xx.x%) | xx (xx.x%) | xx (xx.x%) | xx (xx.x%) |
| | Vomiting | xx (xx.x%) | xx (xx.x%) | xx (xx.x%) | xx (xx.x%) | xx (xx.x%) |
| | Hematemesis (vomiting blood) | xx (xx.x%) | xx (xx.x%) | xx (xx.x%) | xx (xx.x%) | xx (xx.x%) |
| | Hematochezia (anal or rectal bleeding) | xx (xx.x%) | xx (xx.x%) | xx (xx.x%) | xx (xx.x%) | xx (xx.x%) |
| | Positive FOBT | xx (xx.x%) | xx (xx.x%) | xx (xx.x%) | xx (xx.x%) | xx (xx.x%) |
| | Decrease in hematocrit of at least 10 % points | xx (xx.x%) | xx (xx.x%) | xx (xx.x%) | xx (xx.x%) | xx (xx.x%) |
| | Decrease in hemoglobin by at least 20 g/dL | xx (xx.x%) | xx (xx.x%) | xx (xx.x%) | xx (xx.x%) | xx (xx.x%) |
| | Increase in BUN \geq 40 mg/dL | xx (xx.x%) | xx (xx.x%) | xx (xx.x%) | xx (xx.x%) | xx (xx.x%) |
| | Increase in creatinine \geq 1.8 mg/dL | xx (xx.x%) | xx (xx.x%) | xx (xx.x%) | xx (xx.x%) | xx (xx.x%) |
| | Increase in ALT \geq 3 ULN | xx (xx.x%) | xx (xx.x%) | xx (xx.x%) | xx (xx.x%) | xx (xx.x%) |
| | Increase in AST \geq 3 ULN | xx (xx.x%) | xx (xx.x%) | xx (xx.x%) | xx (xx.x%) | xx (xx.x%) |

Table 5: Summary of Blood Chemistries

| | Kindolor 100 mg | Kindolor 300 mg | Kindolor xx mg | Placebo |
|--|-----------------|-----------------|----------------|-------------|
| | (N=xx) | (N=xx) | (N=xx) | (N=xx) |
| Repeat for each visit: Screening, Day -1, discharge and follow-up | | | | |
| Test Name (units) | | | | |
| N | xx | xx | xx | xx |
| Mean (SD) | xx.x (xx.x) | xx.x (xx.x) | xx.x (xx.x) | xx.x (xx.x) |
| Min - Max | xx-xx | xx-xx | xx-xx | xx-xx |
| Change from baseline at discharge and follow-up | | | | |
| N | xx | xx | xx | xx |
| Mean (SD) | xx.x (xx.x) | xx.x (xx.x) | xx.x (xx.x) | xx.x (xx.x) |
| Min - Max | xx-xx | xx-xx | xx-xx | xx-xx |

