| | Mean (SD) | xx.x (xx.x) | xx.x (xx.x) | xx.x (xx.x) | xx.x (xx.x) |
| | Min - Max | xx-xx | xx-xx | xx-xx | xx-xx |
| | | | | | |
| Fecal Occult Blood Test (FOBT) | Negative | xx (xx.x%) | xx (xx.x%) | xx (xx.x%) | xx (xx.x%) |
| | Positive | xx (xx.x%) | xx (xx.x%) | xx (xx.x%) | xx (xx.x%) |
| | Invalid | xx (xx.x%) | xx (xx.x%) | xx (xx.x%) | xx (xx.x%) |
| | | | | | |
| Glucose | Negative | xx (xx.x%) | xx (xx.x%) | xx (xx.x%) | xx (xx.x%) |
| | Positive | xx (xx.x%) | xx (xx.x%) | xx (xx.x%) | xx (xx.x%) |

Programmers note: Repeat for collected tests. Continuous tests should be summarized using mean, sd, range.

Table 21: Summary of Positive Pregnancy and Urine Drug Tests

| | Number positive (%) | | | |
|--|---------------------|--------------------|-------------------|------------|
| | Kindolor 100 mg | Kindolor 300 mg | Kindolor xx mg | Placebo |
| Test | (N=xx) | (N=xx) | (N=xx) | (N=xx) |
| Repeat for each visit: Screening, Day -1, discharge and follow-up | | | | |
| Amphetamine | xx (xx.x%) | xx (xx.x%) | xx (xx.x%) | xx (xx.x%) |
| Barbiturates | xx (xx.x%) | xx (xx.x%) | xx (xx.x%) | xx (xx.x%) |
| Benzodiazepines | xx (xx.x%) | xx (xx.x%) | xx (xx.x%) | xx (xx.x%) |
| Cocaine | xx (xx.x%) | xx (xx.x%) | xx (xx.x%) | xx (xx.x%) |
| Opiates | xx (xx.x%) | xx (xx.x%) | xx (xx.x%) | xx (xx.x%) |
| cannabinoids | xx (xx.x%) | xx (xx.x%) | xx (xx.x%) | xx (xx.x%) |
| phencyclidine | xx (xx.x%) | xx (xx.x%) | xx (xx.x%) | xx (xx.x%) |
| propoxyphene | xx (xx.x%) | xx (xx.x%) | xx (xx.x%) | xx (xx.x%) |
| methadone | xx (xx.x%) | xx (xx.x%) | xx (xx.x%) | xx (xx.x%) |
| Pregnancy Test | xx (xx.x%) | xx (xx.x%) | xx (xx.x%) | xx (xx.x%) |

Table 22: Summary of Shift from Baseline – Chemistry Tests

| | | | | Post-Baseline | | |
|-----------------|-----------------|--|----------|---------------|------------|------------|
| Treatment Group | Test | Visit | Baseline | Low | Normal | High |
| | Lab test (Unit) | Repeat for each visit: discharge and follow-up | Low | xx (xx.x%) | xx (xx.x%) | xx (xx.x%) |
| | | | Normal | xx (xx.x%) | xx (xx.x%) | xx (xx.x%) |
| | | | High | xx (xx.x%) | xx (xx.x%) | xx (xx.x%) |

Table 23: Summary of Shift from Baseline – Hematology Tests

| | | | | Post-Baseline | | |
|-----------------|-----------------|--|----------|---------------|------------|------------|
| Treatment Group | Test | Visit | Baseline | Low | Normal | High |

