| | Lab test (Unit) | Repeat for each visit: discharge and follow-up | Low | xx (xx.x%) | xx (xx.x%) | xx (xx.x%) |
| | | | Normal | xx (xx.x%) | xx (xx.x%) | xx (xx.x%) |
| | | | High | xx (xx.x%) | xx (xx.x%) | xx (xx.x%) |

Table 24: Summary of Shift from Baseline – Coagulation Tests

| | | | | Post-Baseline | | |
|-----------------|-----------------|--|----------|---------------|------------|------------|
| Treatment Group | Test | Visit | Baseline | Low | Normal | High |
| | Lab test (Unit) | Repeat for each visit: discharge and follow-up | Low | xx (xx.x%) | xx (xx.x%) | xx (xx.x%) |
| | | | Normal | xx (xx.x%) | xx (xx.x%) | xx (xx.x%) |
| | | | High | xx (xx.x%) | xx (xx.x%) | xx (xx.x%) |

Table 25: Summary of Vital Signs

| | Kindolor 100 mg | Kindolor 300 mg | Kindolor xx mg | Placebo |
|---|-----------------|-----------------|----------------|-------------|
| | (N=xx) | (N=xx) | (N=xx) | (N=xx) |
| Repeat for each visit: Screening, Day -1, Treatment, Inpatient Follow-up, Clinic Discharge, Outpatient Follow-up and Early termination | | | | |
| Test Name (units) | | | | |
| N | xx | xx | xx | xx |
| Mean (SD) | xx.x (xx.x) | xx.x (xx.x) | xx.x (xx.x) | xx.x (xx.x) |
| Min - Max | xx-xx | xx-xx | xx-xx | xx-xx |
| Change from baseline | | | | |
| N | xx | xx | xx | xx |
| Mean (SD) | xx.x (xx.x) | xx.x (xx.x) | xx.x (xx.x) | xx.x (xx.x) |
| Min - Max | xx-xx | xx-xx | xx-xx | xx-xx |

Programmers note: vital signs include heart rate (sitting), blood pressure (sitting), respiratory rate, oral temperature

Table 26: Summary of ECG Results

| | Kindolor 100 mg | Kindolor 300 mg | Kindolor xx mg | Placebo |
|---|-----------------|-----------------|----------------|-------------|
| Result | (N=xx) | (N=xx) | (N=xx) | (N=xx) |
| Repeat for each visit: Screening, Day -1, Treatment, Inpatient Follow-up, Clinic Discharge, Outpatient Follow-up and Early termination | | | | |
| Parameter (units) | | | | |
| N | xx | xx | xx | xx |
| Mean (SD) | xx.x (xx.x) | xx.x (xx.x) | xx.x (xx.x) | xx.x (xx.x) |
| Min - Max | xx-xx | xx-xx | xx-xx | xx-xx |
| Change from baseline | | | | |
| N | xx | xx | xx | xx |
| Mean (SD) | xx.x (xx.x) | xx.x (xx.x) | xx.x (xx.x) | xx.x (xx.x) |
| Min - Max | xx-xx | xx-xx | xx-xx | xx-xx |
| | | | | |
| Interpretation | | | | |
| Normal | xx (xx.x%) | xx (xx.x%) | xx (xx.x%) | xx (xx.x%) |
| Abnormal, Not Clinically Significant | xx (xx.x%) | xx (xx.x%) | xx (xx.x%) | xx (xx.x%) |

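### The SAP's laboratory summary and shift-table shells leave out the early-termination visit, so a subject who leaves before the Day 3 draw has no post-dose value in them

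*SAP*

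**What the plan says.** The safety analysis set is every subject who received a dose (SAP section 4), and clinical laboratory data are a listed safety endpoint (SAP 3.3).

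- **When laboratory tests are taken.** In the schedule of visits (SAP Table 1, matching the protocol schedule), serum amylase, serum lipase, chemistry, hematology, coagulation and urinalysis are marked at screening, Day -1, Day 3 discharge, outpatient follow-up and early termination. None is marked on Day 1 or Day 2. Protocol 8.13.1 says that, when a subject withdraws or is discontinued, "laboratory analyses, Stool Consistency Questionnaire, GI Symptoms Checklist, and AEs will be performed as soon as possible after discontinuation from the study".
- **Extra tests.** Protocol 11.3 states "Additional laboratory samples may be taken at the discretion of the investigator" when results are out of range or symptoms call for it.
- **What the SAP text promises.** SAP 9.7 says that laboratory results "will be reported as summary statistics for each assessment time point".
- **What the laboratory shells contain.** In SAP section 12, Tables 17-20 carry the line "Repeat for each visit: Screening, Day -1, discharge and follow-up", and Tables 17, 18 and 20 have a block labelled "Change from baseline at discharge and follow-up". (The blood chemistry shell is Table 17 in the list of tables, although its own caption shows another number.) Shift Tables 22-24 carry "Repeat for each visit: discharge and follow-up".
- **What the other safety shells contain.** Vital signs and ECG (Tables 25 and 26) carry "Repeat for each visit: Screening, Day -1, Treatment, Inpatient Follow-up, Clinic Discharge, Outpatient Follow-up and Early termination". The stool and GI symptom shells (Tables 15 and 16) also name early termination.

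**The concern.** Programmers build from shells. Here the shells name their visits one by one, and the list omits a visit at which laboratory tests are planned. Because nothing is scheduled on Days 1 and 2, the early-termination draw is the only scheduled post-dose laboratory assessment for a dosed subject who leaves before the Day 3 draw. That subject would be counted in the column N with a baseline value, but would have no row after dosing.

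The loss is unlikely to be random. Subjects may leave, or be redrawn, because they feel unwell or have a worrying result. Leaving those values out tilts the laboratory summaries towards showing no effect, in a study whose primary objective is safety. With six active subjects per dose, a single subject matters.

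Unscheduled results raise the same problem without any withdrawal. SAP 9.7 does not say how they are used, and SAP 9.10 deals only with adverse event data and dates. A value that is abnormal on Day 2 and normal on Day 3 would appear in no shift table.

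**Working it through.** **Step 1: the plan's own figure.** The protocol (12.4) and SAP (section 7) give the chance of seeing at least one event among 6 active subjects. The formula is 1 - (1 - p)^n.

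- p = 10%: 1 - 0.90^6 = 46.9% (stated 47%)
- p = 15%: 1 - 0.85^6 = 62.3% (stated 62%)
- p = 20%: 1 - 0.80^6 = 73.8% (stated 74%)
- p = 25%: 1 - 0.75^6 = 82.2% (stated 82%)

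The figures reproduce. They describe adverse events rather than shell coverage, and serve here only as a scale for what six subjects can show.

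**Step 2: schedule against shells (post-dose visits).**

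| Assessment | Scheduled at early termination | Early termination in shell |
|---|---|---|
| Chemistry, amylase, lipase (Tables 17, 22) | Yes | No |
| Hematology (Tables 18, 23) | Yes | No |
| Coagulation (Tables 19, 24) | Yes | No |
| Urinalysis (Table 20) | Yes | No |
| FOBT (Table 20) | No | No |
| Stool questionnaire (Table 15) | Yes | Yes |
| Vital signs, ECG (Tables 25, 26) | Yes | Yes |

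The mismatch is confined to the laboratory shells. The SAP gives no rule for assigning an early-termination draw to discharge or follow-up, so nothing else in it brings the value back in.

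**Step 3: size, as an illustration.** Assume that one active subject in a dose group leaves after dosing and before the Day 3 draw, and has only early-termination laboratory results.

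- If that subject holds the group's only high value, the full data show 1/6 = 16.7% and the shell shows 0/5 = 0%.
- Protocol 8.13.1 allows a replacement to be considered for an active subject who leaves before Day 3 release. With a replacement whose value is normal, the full data show 1/7 = 14.3% and the shell shows 0/6.
- With n = 5 in the shell, the Step 1 probabilities become 41.0%, 55.6%, 67.2% and 76.3%. With n = 4 (two such subjects) they become 34.4%, 47.8%, 59.0% and 68.4%.

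The documents give no withdrawal rate, so no frequency is attached to this scenario.

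**Step 4: where the values would still appear.**

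- SAP 9.1 says all data are listed, and Listings 19-21 cover chemistry, hematology and coagulation. There is no urinalysis listing among the 25 shells, and the Listing 20 shell names Day 4 and Weeks 4, 8 and 12, which are not visits in this study.
- Protocol 11.1.4 and 11.3 send abnormal or clinically significant results to adverse event reporting with a severity grade. The adverse event tables have no visit restriction, but they show neither the value nor its shift from baseline.
- Table 16 names early termination and covers hematocrit, hemoglobin, BUN, creatinine, ALT and AST thresholds. It has no row for bilirubin, amylase, lipase, platelets or coagulation. Its hemoglobin row reads a fall of 20 g/dL, against 2 g/dL in protocol 11.1.5 and Appendix B.

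**The case against.** The strongest reply is that the governing text is already right. SAP 9.7 covers every time point, the SAP introduction calls its outputs sample tables, and no rule excludes early leavers or unscheduled results. The affected subject must also leave within about 48 hours of a single dose, despite confinement through Day 3 (protocol 8.6.1). This limits how often the gap will bite. It does not remove the gap: text and shells disagree, and the visit list is explicit.

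On unscheduled results, Tables 25 and 26 have no such row either. A repeat to verify an out-of-range value does not delete the scheduled value. What remains is the extra draw between scheduled visits, for which the SAP has no rule.

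Several stronger readings are tempting, and the documents do not support them:

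- A reader might infer that the laboratory tables describe completers only. They are by-visit summaries of observed values on all dosed subjects. Someone who leaves after the Day 3 draw still contributes the discharge value, and Tables 17-20 keep pre-dose values.
- A reader might infer that early-termination FOBT results are left out. FOBT is not marked at early termination and is not in the 8.13.1 list, so Table 20 omits no planned test. Table 16 has a positive-FOBT row that covers early termination.
- A reader might infer that an omitted value survives only in a listing. Step 4 shows that a clinically significant value would ordinarily also reach the adverse event tables.
- A reader might infer that a stopping-level value is hidden, or that an escalation decision would change. The shift tables classify low, normal and high, so they could not show a Grade 3 value even with the extra row. Safety review is continuous, with ad hoc DSMB meetings if stopping criteria are met (protocol section 10).
- A reader might infer that the cohort tables for the DSMB share the omission. They follow an operating charter that is not among the documents, so this is not established.

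**Conclusion.** The concern holds as a mismatch between the laboratory shells and both the schedule and SAP 9.7. Followed as written, Tables 17-20 and 22-24 give no post-dose laboratory value for a dosed subject who leaves before the Day 3 draw, and the shift tables miss an abnormal unscheduled value that has normalised by Day 3. The effect is limited to summary and shift tables.

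The 0/5 against 1/6 contrast rests on three assumptions: one active subject leaves in that window, that subject is not replaced, and that subject holds the group's only high value. It shows what the shells could conceal in a group of six and is not a forecast. The correction is worth making before the tables are programmed, because the data are already collected and any omitted values may be missing for reasons related to safety.

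**What to change.** 1. In SAP Tables 17-19 and the urinalysis part of Table 20, add early termination to the repeated visits and to the change-from-baseline rows.
2. In shift Tables 22-24, add early termination to the repeated visits.
3. In Tables 22-24, add one row for the worst post-baseline value, by dose group and pooled placebo. It should draw on scheduled, early-termination and unscheduled results, with the direction of worst stated for each test. The denominator is the number of subjects with any post-dose value.
4. In SAP 9.7, add a sentence saying how repeat and unscheduled results are used in the by-visit rows and in the worst-value row.

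The cost is shell wording and minor programming. No new data, visits or subjects are needed.
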